Two randomized controlled trials (RCT) with somewhat similar study design assessed the efficacy of BoNT in hand ET (Jankovic et al. 1996; Brin et al. 2001) (Figure 1). Both trials used type-A BoNT (Botox®). Both trials investigated injections in wrist flexors and extensors. Injections with two strengths, 50U and 100U, were tested. The dose injected in wrist extensors was always two-third (2/3rd) of that injected in wrist flexors. But there were also some differences in trial designs. Figure 1 depicts the differences.

Figure 1

Randomized control trial 1 (Jankovic et al. 1996)	Randomized control trial 2 (Brin et al. 2001)
Comparison: BoNT versus placebo	Comparison: BoNT 50U versus 100U versus placebo
Sites: wrist flexors and extensors of dominant hand	Random assignment to a comparison group
Regimen: 50U in flexor and extensor (15 flexor carpi radialis (FCR), 15 flexor carpi ulnaris (FCU), 10 extensor carpi radialis longus and bravis (ECR), 10 extensor carpi ulnaris (ECU)) → if unsuccessful at 4 week evaluation, then double the dose at each injection site.	Site: Wrist flexor and extensor of dominant hand (FCR, FCU, ECR, ECU).
Follow-up: 2,4,6,8,12,16 weeks	Regimen: 50U = 15 FCR, 15 FCU, 10 ECR, 10ECU 100U = 30 FCR, 30 FCU, 20 ECR, 20ECU
	Follow-up: 1,2,4,6,8,12,16 weeks

Both trials reported significant improvement in tremor rating scale and objective assessment using accelerometry (Jankovic et al. 1996; Brin et al. 2001). One study reported that 75% of BoNT treated patients had mild to moderate improvement that reached statistical significance (Jankovic et al. 1996). Objective assessment of ET with limb accelerometry showed a 30% reduction in tremor intensity in 9 of 12 BoNT-treated patients and in 1 of 9 placebo-treated patients ($p < 0.05$) (Jankovic et al. 1996). Similar results were reproduced in a second RCT with much larger ($n=133$) number of ET patients (Brin et al. 2001). Results of these two RCTs led to the American Academy of Neurology level-B recommendation that BoNT should be considered for treatment of ET in patients who are refractory to oral pharmacotherapy (Simpson et al. 2008).

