In summary, while these studies have demonstrated the potential role of BoNT for ET there remains limitations that have yet to be addressed. It is unclear if the perceived efficacy of BoNT in tremor reduction is diminished by associated extensor weakness. It is also unclear if BoNT injection of flexors alone is equally efficacious as the injection of both flexor and extensor muscles. If injecting extensor muscles is essential, can the ratio between extensor and flexor muscles be adjusted to give efficacy with no weakness? Furthermore, although previous studies have demonstrated significant objective improvement in tremor severity, they did not observe significant improvements in quality of life (QOL), functional improvement, and global improvement.

With these limitations in mind, we propose a pilot, single center, double blind, randomized, parallel, placebo controlled trial comparing 2 BoNT injection patterns for treatment of moderate to severe essential tremor. To minimize the potential for extensor weakness, we will inject the extensor muscles with 1/3 the dose used for the flexor muscles (a 3:1 ratio of BoNT injected for flexor to extensor as compared to the previous studies which used a 3:2 ratio). Our primary outcome and secondary outcomes as detailed below will include patient global impression scale as well as other functional and QOL scales.

6) STUDY OBJECTIVES:

Study aim:

To compare the efficacy of botulinum toxin (BoNT) injections in forearm flexors plus extensor muscles versus flexors alone for the treatment of essential hand tremor (ET).

Hypothesis:

We hypothesize that both patterns of BoNT injection (flexors plus extensors, flexors alone) will be equally efficacious in decreasing tremor, but that patients in the flexors alone group will experience less motor weakness and therefore report greater global improvement in symptoms.

We acknowledge the possibilities that patients in the flexors plus extensors group may perceive greater improvement in tremor severity due to the additional injection of the extensor compartment and that the injection of the extensor compartment may be well tolerated because the injected dose is only 1/3 of the dose for the flexor compartment.

Primary Outcome Measure:

Difference in 6 week post injection on a Patient Global Impression Scale-Improvement Subscale (PGI-I)

Secondary Outcome Measures:

1. *Improvement in 6 week post injection in tremor rating scale.*

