2. *Difference in the mean Quality of Life in Essential Tremor Questionnaire (QUEST) at Week 6 from baseline between wrist flexors versus wrist flexors plus extensors group.*
3. *Improvement in 6 week post injection in Clinician Global Impression Scale-Improvement Subscale (CGI-I).*
4. *Difference in grip strength post injection between the two groups at 6 weeks*
5. *12 week post injection patient global improvement scale*

6. *12 week post injection tremor rating scale*
7. *Difference in the mean QUEST score at Week 12 from baseline between wrist flexors versus wrist flexors plus extensors group.*
8. *12 week post injection clinician global improvement scale*
9. *Difference in grip strength post injection between the two groups at 12 weeks.*

Tertiary Outcome Measures

1. *Monitor changes in depression using PHQ-9 at 6 weeks*
2. *Monitor changes in anxiety using GAD-7 at 6 weeks*
3. *Monitor changes in depression using PHQ-9 at 12 weeks*
4. *Monitor changes in anxiety using GAD-7 at 12 weeks*

The scales that will be used in the study are below:

Global assessment graded by patient and clinician (PGIS and CGIS respectively) on -4 to +4 scale

- -4 = severe worsening
- 0 = no change
- +4 = complete abolishment of symptoms

Tremor Rating scale (TRS) at rest, posture and kinetic

- 0 = none perceived
- 1 = slight (barely noticeable)
- 2 = moderate, noticeable, probably not disabling (<2cm excursions from affected part)
- 3 = marked, probably partially disabling (2-4cm excursions)
- 4 = severe, coarse, disabling (>4cm excursion)

Kinetic tremor will be measured using motor tasks including handwriting and pouring. Patients will be asked to write the sentence "Today is a nice day" with their dominant hand. They will also be asked to draw a spiral. Pouring will be assessed by asking the patient to pour water from one cup to another.

QUEST will also be administered at baseline and follow up visits to assess functional impairment of tremor in activities of daily living.

Grip strength will be assessed using dynamometer.

7) STUDY DESIGN/METHODS:

We propose a pilot, single center, double blind, randomized, parallel, placebo controlled trial comparing 2 BoNT injection patterns for treatment of moderate to severe essential tremor.

We will recruit 20 patients with ET. The following inclusion and exclusion criteria will be used during the screening visit.

Inclusion Criteria

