- Group 2 – Flexors alone: BoNT 150 units total (75U FCR, 75U FCU, 0UECR, 0U ECU).

The patients will be seen in follow up at 6 weeks and again at 12 weeks. At these times we will repeat all baseline measures and in addition have patients evaluate treatment response using a patient global impact scale ranging from -4 (severely worse) to +4 (no more tremor) with 0 meaning no change. Clinicians will be asked to complete the same scale. Figure 2 depicts the outline of our study design.

Figure 2: Study Design

Visit	1	2	3
Type	Screening/Baseline (injection)	Post injection week	Post injection week
Time	0	6 weeks	12 weeks
Informed Consent	X		
History and PE	X	X	X
Concomitant Meds	X	X	X
Adverse Events		X	X
TRS	X	X	X
QUEST	X	X	X
PHQ-9	X	X	X
GAD-7	X	X	X
PGIS		X	X
CGIS		X	X
Grip Strength	X	X	X

Procedure/test:

The BoNT injections will take place in a dedicated clinical research space, located in the CNR Movement Disorders clinic in the U ("Mellen") building. No other patient will be present and the door will be closed to protect patient privacy. The patients will come in the morning when tremor will be evaluated clinically. Each patient will receive BoNT injections into dominant upper extremity using protocol outlined above. We will evaluate patients at week 6 and 12 post injection. At baseline visit, the nurse who is mixing the toxin will not be blinded to the treatment arm, but both the patient and PI who will be injecting as well as administering the rating scale will remain blind.

Randomization will be done using a computer program and each subject will be assigned an envelope which nurse will have access to and open when she is mixing the agent.

Statistical analysis:

Assessment of tremor improvement - We will compare average result of PGIS and CGIS at week 6 and week 12 between two groups. Furthermore we will compute percent change of TRS and QUEST for each follow-up visit as compared to the baseline. Given the small sample size, Mann-Whitney U test will be used for calculations.

Based on the previous studies (Jankovic et al. 1996; Brin et al. 2001), mean change in TRS and PGIS was 1 point (about 25% improvement on a 4-point scale) with a standard deviation of 0.7 points at week 6 post injection. To achieve an alpha of 0.05 and a power of 80%, we estimate a sample of size of 18 total patients with 9 in each treatment group. Accounting for an estimated 10% attrition rate we will recruit 20 total patients into this trial.

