We will use the above analysis to answer our primary question: Whether BoNT injections to both wrist flexors and extensors are superior as compared to injections to wrist flexors alone; or vice versa?

Confidentiality of Data:

Identifying information will be severed from study data. Subject numbers will be used to identify all participants. A password protected file linking subject numbers to identifying information will be maintained on a CNR computer. Likewise, electronic study data will be stored in password protected files and folders on a CNR computer. Any data on portable or removable device will be de-identified and protected by encryption. Paper study forms will be maintained in a locking filing cabinet in a secure area. Only the study investigators will have access to study files and folders.

Safety and Data Monitoring:

All adverse events, as reported by the subject during the study, will be documented and reported to the IRB according to the IRB policy. Any unanticipated problems will be reported to the IRB according to the IRB policy as soon as they occur or as soon as they are discovered. Efficacy data will be collected as per study protocol

Budget:

For a total of 20 patients and 3 visits per patient (Baseline, 6 weeks post injection and 12 weeks post injection) including investigator, coordinator, supplies and patient stipend we anticipate a total cost of \$48, 423. Funding will be provided by Ipsen, the manufacturer of Dysport®.

Reference List

Larson, P. S. (2014). Deep brain stimulation for movement disorders. *Neurotherapeutics : The Journal of the American Society for Experimental NeuroTherapeutics*, 11(3), 465–74. doi:10.1007/s13311-014-0274-1

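### The 80% power for the week 6 PGI-I is unsupported: its 1-point, SD 0.7 input is not reconciled with the Background, and the planned Mann-Whitney test falls short of 80% even at those values

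*Combined protocol and SAP*

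**What the plan says.** Section 6 makes the patient-rated PGI-I at week 6 the primary outcome. The same section defines the scale: "Global assessment graded by patient and clinician (PGIS and CGIS respectively) on -4 to +4 scale". Each TRS item runs from 0 to 4.

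Section 7 (Statistical analysis) opens the sample-size paragraph with "Based on the previous studies", cites the two earlier placebo-controlled trials, and continues: "mean change in TRS and PGIS was 1 point (about 25% improvement on a 4-point scale) with a standard deviation of 0.7 points". The time point given for these figures is six weeks after injection. From this it derives 9 patients per arm (18 in total) for alpha 0.05 and 80% power, and 20 recruited after 10% attrition. The paragraph before it names the Mann-Whitney U test for the analysis. The primary question that the analysis must answer is two-directional: "Whether BoNT injections to both wrist flexors and extensors are superior as compared to injections to wrist flexors alone; or vice versa".

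Section 5 (Background), in its closing summary, accepts that the previous studies showed objective improvement in tremor severity but adds that "they did not observe significant improvements in quality of life (QOL), functional improvement, and global improvement".

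**The concern.** One mean and one SD serve both a clinician-rated severity score and a patient's single judgement of improvement. No PGIS-specific figure appears anywhere, and the pair is attributed to trials that the Background describes as showing no significant global improvement. A 1-point PGIS change with SD 0.7 is a large, tight effect, so the two statements need explaining together.

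The sample size and the 80% power for the primary outcome rest on this pair. If the power is in fact lower, a null result is more likely than the plan implies. A reader relying on the 80% figure could then take that result as evidence that the two injection patterns work equally well.

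**Working it through.** **Inputs.** Difference 1 point, SD 0.7, alpha 0.05, 9 per arm, 10% attrition, Mann-Whitney test (all Section 7). Sidedness is not stated; I assume two-sided because the primary question runs both ways. The SDs of 1.0 and 1.4 are my assumptions, used to show sensitivity.

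**1. The plan's own figure.** For a two-sample t-test, power comes from the noncentral t with noncentrality Δ / (SD × √(2/n)). With Δ = 1, SD = 0.7 and n = 9 this is 1 / (0.7 × 0.471) = 3.03 on 16 degrees of freedom, giving power 81.2%. Solving for 80% gives n = 8.76, so 9 per arm and 18 in total; 18 / 0.9 = 20. The stated numbers reproduce as a t-test calculation.

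**2. Section 7 against Section 5.** The only group sizes that the documents give for the smaller earlier trial are 12 toxin and 9 placebo patients. These are accelerometry counts, so using them for PGIS is an assumption.
- Within the toxin arm: t = 1 / (0.7/√12) = 4.95, p = 0.0004 against zero.
- As a difference from placebo: t = 1 / (0.7 × √(1/12 + 1/9)) = 3.24, p = 0.004.
- Smallest significant difference at SD 0.7: 2.093 × 0.7 × √(1/12 + 1/9) = 0.65 points.

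A non-significant global result therefore needs one of two things:
- A PGIS SD above about 0.7 / 0.646 = 1.08, if 1 point is the difference from placebo.
- Placebo improvement of more than about 1 − 0.65 = 0.35 points, if 1 point is a within-arm change and SD 0.7 is right.

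The first removes the SD on which the power rests. The second means that the 1 point is not a between-group difference, which is what a two-arm calculation requires.

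**3. Sensitivity of power, 9 per arm, 1-point difference.** The Mann-Whitney figures are simulated (20,000 trials per setting). The lower value at SD 0.7 is for scores rounded to the integer scale (asymptotic test); the higher is for continuous normal data (exact test).

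| SD | Noncentrality | t-test | Mann-Whitney |
|---|---|---|---|
| 0.7 | 3.03 | 81% | about 72-76% |
| 1.0 | 2.12 | 51% | about 45% |
| 1.4 | 1.52 | 30% | about 25% |

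**4. Detectable difference.** The t-test reaches 80% at 1.41 SD. The Mann-Whitney test at that difference gives about 75% on continuous data. A repeat simulation (40,000 trials) at 1.5 SD gave about 80% on continuous data and 76-80% on rounded scores. In points, 1.5 SD is 1.5 × 0.7 = 1.05, 1.5 × 1.0 = 1.5, or 1.5 × 1.4 = 2.1.

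**The case against.** The strongest defence is that nothing here is an arithmetic error: 9, 18 and 20 follow from the stated inputs. That stands. The dispute is over the inputs and over the test for which the power was computed.

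Several stronger readings are tempting, and the documents do not support them.

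- *The two sections contradict each other.* They are in tension only. A mean change reads naturally as within-arm, and it can coexist with no significant difference from placebo. Section 5 also reports that 75% of treated patients in one trial had mild to moderate improvement that reached significance, without naming the scale.
- *The PGIS is twice as long, so its SD must be larger.* This does not follow. Change on a 0-4 TRS item can itself run from -4 to +4, and 1 point is a quarter of the improvement half of the PGIS. SD 1.4 is therefore illustrative, not derived.
- *The SD of 0.7 is wrong.* The plan cites a source that cannot be checked here. The value is unverified.
- *A null result is near-certain.* Power of 30-51% for 1 point at the larger SDs makes a null result more likely than the plan implies, but not near-certain.
- *The week 6 figure is inflated by re-dosing.* One earlier trial's regimen was "if unsuccessful at 4 week evaluation, then double the dose at each injection site". The documents give neither size nor direction for any effect of this on the week 6 values, so nothing here rests on it.

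It is also fair to say that this is a declared pilot, and that if all 20 patients complete, Mann-Whitney power at the stated inputs is about 78-82%. But the plan makes its claim for 18 completers, and that allowance does nothing for the uncertainty in the inputs.

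**Conclusion.** The concern holds in this form: the 80% power for the primary week 6 PGI-I comparison is not supported as written. On either way of reconciling Sections 5 and 7, the 1-point, SD 0.7 pair is not an established input for a between-arm PGI-I difference. Separately, with the planned test and 9 per arm, power at the stated inputs is about 72-76%, not 80%. It falls to about 45% at SD 1.0 and 25% at SD 1.4.

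This rests on a two-sided test, normally distributed underlying scores in the simulation, assumed values for the larger SDs, and accelerometry counts as stand-ins for PGIS group sizes in the consistency check. The Mann-Whitney shortfall at SD 0.7 does not depend on the last two.

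**What to change.** Amend the sample-size paragraph in Section 7:

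1. Reconcile the PGIS attribution with the Background. Say whether the 1 point is a within-arm change or a difference from placebo, on which scale, and how it fits with no significant global improvement.
2. Label 1 point and SD 0.7 as planning assumptions for the between-arm PGI-I difference.
3. Replace the 80% claim with a detectable difference under the planned test: 9 completers per arm give about 80% power for about 1.5 SD, that is about 1.05, 1.5 or 2.1 points if the SD is 0.7, 1.0 or 1.4. Show the power for 1 point across the same SDs.
4. State that a null result does not show that the two patterns are equivalent.

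Keep n = 20. The cost is a few sentences and a less favourable stated power; no extra patients, visits or assessments are needed.

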APPENDIX

Scales

FLEXd-ET

Tremor Rating Scale

Subject ID _____

Visit number _____

Dominant Hand _____

Please use below grading for items 1-3

- 0 = none perceived
- 1 = slight (barely noticeable)
- 2 = moderate, noticeable, probably not disabling (<2cm excursions from affected part)
- 3 = marked, probably partially disabling (2-4cm excursions)
- 4 = severe, coarse, disabling (>4cm excursion)

1. At Rest _____
2. Posture (arms 90° perpendicular in front of patient) _____
3. Action/Intention (Finger to nose) _____
4. Handwriting (Please write *Today is a nice day in line below*) _____

0 = Normal

1 = Mildly abnormal

2 = Moderately abnormal. Legible, but with considerable tremor

3 = Marked abnormal. Illegible

4 = Severely abnormal. Unable to keep pencil or pen on paper without holding down with other hand

5. Spiral drawings (on back of sheet) _____

0 = normal

1 = Slightly tremulous. May cross lines occasionally

2 = Moderately tremulous or crosses line frequently

3 = Accomplishes task with great difficulty. Many errors

4 = Unable to complete drawing

6. Pouring _____

0 = normal

1 = more careful, but no water spilled

2 = spills a small amount of water (up to 10% of total amount)

3 = Spills a considerable amount (>10-50% of total amount)

4 = Unable to pour water without spilling most of the water

FLEXd-ET

Patient Global Impression Scale

Subject ID _____

Visit number _____

Dominant Hand _____

Please circle which number best corresponds to overall improvement in symptoms after injection

Severely worse

No Change

No further symptoms

-4 -3 -2 -1 0 +1 +2 +3 +4

FLEXd-ET

Clinician Global Impression Scale

Subject ID _____

Visit number _____

Dominant Hand _____

Please circle which number best corresponds to overall improvement in symptoms after injection

Severely worse

No Change

No further symptoms

-4 -3 -2 -1 0 +1 +2 +3 +4

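### Does 9 per arm fall short of the stated 80% power once the planned Mann-Whitney test is applied to whole-number PGI-I scores?

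*Combined protocol and SAP*

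**What the plan says.** The sample-size paragraph (section 7, Statistical analysis) takes its inputs from two earlier trials: "mean change in TRS and PGIS was 1 point (about 25% improvement on a 4-point scale"), with an SD of 0.7 at week 6. It then states "a power of 80%, we estimate a sample of size of 18 total patients with 9 in each treatment group", and allows for 10% attrition to reach 20 recruits. That sentence gives alpha as 0.05 but no test and no sidedness.

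The paragraph just before it names the test: "Given the small sample size, Mann-Whitney U test will be used for calculations". It does not say whether the p-value is exact or large-sample, or whether a continuity correction applies. The primary question that closes the section asks whether injections to both muscle groups "are superior as compared to injections to wrist flexors alone; or vice versa", which is open in both directions.

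The primary outcome (section 6) is the week-6 PGI-I. Section 6 describes the scale as "Global assessment graded by patient and clinician (PGIS and CGIS respectively) on -4 to +4 scale". The Appendix form tells the patient: "Please circle which number best corresponds to overall improvement in symptoms after injection", and offers nine whole numbers.

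**The concern.** The figure of 9 per arm is what a two-sided t-test on continuous scores would give, and the plan does not use a t-test. A rank test loses a little power against the t-test when data are normal. Whole-number scores in 18 patients will be heavily tied, and an exact p-value at this size is conservative. If the planned test has less than 80% power, the trial is described as slightly stronger than it is.

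The version of the p-value also matters at this size, because exact, corrected and uncorrected versions can disagree on the same 18 patients. Leaving the version open until after unblinding would leave a small analytic choice in the primary comparison.

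**Working it through.** **Inputs.** From section 7: difference 1 point, SD 0.7, alpha 0.05, 9 per arm, 10% attrition. From the Appendix: integer scores from -4 to +4. The 1 point is taken as a between-arm difference, as the plan's calculation requires. Whether that is the right reading of an earlier mean change is a separate matter.

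**Reproducing the stated figure.**
- Standardised difference: 1/0.7 = 1.43.
- Two-sided t-test: required n = 8.76, so 9 per arm. Power is 75.7% at 8, 81.2% at 9 and 85.5% at 10.
- Normal formula: 2 × (1.960 + 0.842)² × 0.7² / 1² = 7.69 per arm. Divided by a Mann-Whitney efficiency of 0.955 this is 8.05, and by the lower bound of 0.864 it is 8.90. Both round up to 9.
- One-sided t-test: n = 6.85, so 7 per arm, with 89.5% power at 9. The plan's 9 therefore points to two-sided testing, as does the primary question.
- Attrition: 18 / (1 - 0.10) = 20, as stated.

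**Power of the planned test.** With n per arm, N = 2n and tie-group sizes t, the large-sample statistic is z = (|U - n²/2| - c)/s, where s² = (n²/12) × [(N + 1) - Σ(t³ - t)/(N(N - 1))]. Here c = 0 (uncorrected) or 0.5 (continuity-corrected). The exact version uses the permutation distribution given the observed ties.

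Normal scores were rounded to integers, with the underlying SD set to about 0.638 so that the recorded scores have SD 0.7. The lower arm's mean was placed at 0, 0.25 and 0.5. With 40,000 trials per setting, the simulation standard error is about √(0.8 × 0.2/40,000) = 0.002, or 0.2 points.

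| Rounded normal, observed SD 0.7 | Uncorrected | Corrected | Exact |
|---|---|---|---|
| 9 per arm | 79.6-80.3% | 77.8-79.4% | 72.0-73.0% |
| 10 per arm (all 20 evaluable) | 84% | 84% | 78-79% |

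Simulated false-positive rates at 9 per arm were 4.3-4.8%, 4.0-4.1% and 2.6-3.1% respectively, so each version stays below 5% here.

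Two other readings at 9 per arm:
- Continuous normal scores with SD 0.7 give about 79% uncorrected, and 76% corrected or exact.
- If 0.7 is the SD before rounding (observed SD 0.757), power is about 66-73%. This is the less natural reading, since the plan quotes the SD of scores as recorded.

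**Dependence on the score distribution.** The documents give only a mean and an SD. Other integer distributions, shifted by 1 point at 9 per arm (30,000 trials each), give:

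| Shape (SD) | Uncorrected | Corrected | Exact |
|---|---|---|---|
| Three-point symmetric (0.700) | 77.7% | 75.9% | 69.4% |
| Right-skewed, three values (0.700) | 81.2% | 80.0% | 80.1% |
| Heavier-tailed, five values (0.700) | 84.2% | 82.0% | 82.6% |
| Very peaked with outliers (0.693) | 91.2% | 91.2% | 91.2% |

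So 80% is neither a ceiling nor a floor. The gap between p-value versions also depends on shape: about 8 points in the first row, 1 to 2 in the next two and none in the last.

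**Scale of the uncertainty.** Moving the SD from 0.70 to 0.75 alone takes t-test power at 9 per arm from 81% to 76%. That 5-point shift exceeds the shortfall of roughly 1 to 2 points for the continuity-corrected version under rounded-normal scores.

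**The case for a change.** The best argument for a change is that the plan picks a rank test because the sample is small, and in that setting an exact p-value is a natural choice. Under rounded-normal scores, that version has 72-73% power, 7-8 points below the claim. In simulated trials under that assumption, the three versions disagreed on significance in about 7.5-8% of cases, roughly 1 in 13. One sentence fixed before unblinding would remove the ambiguity at almost no cost.

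Part of this stands. The version is not stated, it can matter with heavy ties at 9 per arm, and recording it in advance is good practice. The sample-size sentence could also have named its test.

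The step to a corrected power figure does not stand. The lower numbers need a rounded-normal assumption that the documents do not make, and equally plausible shapes put even the exact version at or above 80%. Replacing 80% with 72-73% or 78-79% would give a new number no better supported than the old one. The choice of version would rest with the investigators in any case, and if they chose the uncorrected large-sample version the stated figure would stand.

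**Conclusion.** The stated power is not an arithmetic error. It reproduces with a two-sided t-test (81.2%). One ordinary version of the planned test also delivers it, to within simulation error, under rounded-normal scores with observed SD 0.7 (79.6-80.3%). The test is named one paragraph earlier, and two-sidedness follows both from the primary question and from the figure of 9 itself.

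What remains is the unstated p-value version. Under rounded-normal scores it moves power by about 7-8 points at 9 per arm; under the skewed and heavier-tailed shapes it moves power by about 2 points or less. Each version kept its false-positive rate below 5% in the null simulations. An analyst will settle this in the ordinary course of programming the test, preferably before unblinding. Recruitment of 20, the endpoint and the design stay as they are whichever version is used, and in a self-described pilot a difference of this size alters no decision.

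This conclusion rests on reading 1 point as the between-arm difference and 0.7 as the SD of the recorded scores. If 0.7 were instead the SD before rounding, power would be about 66-73% under rounded-normal scores, but the plan's wording does not favour that reading.
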